8.4.3 Classification of an Adverse Event

8.4.3.1 Severity of Event

Severity of each AE (grading) will be determined consistent with the Common Terminology Criteria for Adverse Events (CTCAE) version 5.0.

Grade 1 Mild; asymptomatic or mild symptoms, or clinical or diagnostic observations only, or intervention not indicated.

Grade 2 Moderate; minimal, local or noninvasive intervention indicated, or limiting age-appropriate instrumental ADL.

Grade 3 Severe or medically significant but not immediately life-threatening, or hospitalization or prolongation of hospitalization indicated, or disabling, or limiting self-care ADL.

Grade 4 Life-threatening consequences, or urgent intervention indicated.

Grade 5 Death related to AE.

8.4.3.2 Relationship to Study Intervention/Experimental Manipulation

Definitely Related – There is clear evidence to suggest a causal relationship, and other possible contributing factors can be ruled out. The clinical event, including an abnormal laboratory test result, occurs in a plausible time relationship to study procedures administration and cannot be explained by concurrent disease or other drugs or chemicals. The response to withdrawal of the study procedures should be clinically plausible. The event must be pharmacologically or phenomenologically definitive.

Probably Related – There is evidence to suggest a causal relationship, and the influence of other factors is unlikely. The clinical event, including an abnormal laboratory test result, occurs within a reasonable time after administration of the study procedures, is unlikely to be attributed to concurrent disease or other drugs or chemicals, and follows a clinically reasonable response on withdrawal.

Potentially Related – There is some evidence to suggest a causal relationship (e.g., the event occurred within a reasonable time after administration of study procedures). However, other

Abbreviated Title: Mindfulness and Teen Vaping

Version Date: 07/21/2025

NIH IRB#: IRB001855

factors may have contributed to the event (e.g., the participant's clinical condition, other concomitant events). Although an AE may rate only as "possibly related" soon after discovery, it can be flagged as requiring more information and later be upgraded to "probably related" or "definitely related", as appropriate.

Unlikely to be related – A clinical event, including an abnormal laboratory test result, whose temporal relationship to study procedures administration makes a causal relationship improbable (e.g., the event did not occur within a reasonable time after administration of the study procedures) and in which other drugs or chemicals or underlying disease provides plausible explanations (e.g., the participant's clinical condition, other concomitant treatments).

Not Related – The AE is completely independent of study procedures administration, and/or evidence exists that the event is definitely related to another etiology. There must be an alternative, definitive etiology documented by the clinician.

8.4.3.3 Expectedness

A clinician will be responsible for determining whether an adverse event (AE) is expected or unexpected. An AE will be considered unexpected if the nature, severity, or frequency of the event is not consistent with the risk information previously described for the study procedures.

8.4.4 Time Period and Frequency for Event Assessment and Follow-Up

The occurrence of an adverse event (AE) or serious adverse event (SAE) may come to the attention of study personnel during study visits.

All AEs will be captured in the participant's NIDA IRP electronic research record, which is currently, the Clinical Data Warehouse (CDW). Information to be collected includes event description, time of onset, clinician's assessment of severity, relationship to study procedures (assessed only by those with the training and authority to make a diagnosis), and time of resolution/stabilization of the event. All AEs occurring while on study will be documented appropriately regardless of relationship. All AEs except those that are "Not Related" will be followed to adequate resolution/stabilization.

Any medical or psychiatric condition that is present at the time that the participant is screened will be considered as baseline and not reported as an AE. However, if the study participant's condition deteriorates at any time during the study, it will be recorded as an AE.

The events in the table below are very often seen with MRI and therefore fully expected (similar to minor bleeding or bruising after blood draws or injections). They will not be recorded as AEs because their occurrence does not constitute information that would inform or change the established risk profiles of MRI. Events solely related to conditions present at baseline, will also not be recorded as AEs.

Conditions Commonly Associated with MRI and Not to be Recorded as AEs:

| CTCAE Condition | CTCAE Grade | CTCAE Grade Description |
|----------------------------|-------------|--------------------------|
| General disorders: Fatigue | Grade 1 | Fatigue relieved by rest |

Abbreviated Title: Mindfulness and Teen Vaping

Version Date: 07/21/2025

NIH IRB#: IRB001855

| | | |
|--|---------|--|
| Ear and labyrinth disorders: Tinnitus | Grade 1 | Mild symptoms; intervention not indicated |
| Musculoskeletal and connective tissue disorders: Back pain | Grade 1 | Mild pain |
| Nervous system disorders: Dizziness | Grade 1 | Mild unsteadiness or sensation of movement |
| Nervous system disorders: Headache | Grade 1 | Mild pain |

8.4.5 Adverse Event Reporting

In consultation with the PI, a trained member of the study team will be responsible for conducting an evaluation of all adverse events and shall report the results of such evaluation to the NIH Institutional Review Board (IRB) as per [Policy 801](#).

The PI will report all unanticipated adverse device effects (UADEs) to the Sponsor within 10 working days. This should be submitted to the ORSC RSS by a MedWatch Form (Form 3500A), which should be sent ENCRYPTED to the [contact] inbox with a cc to the CD/CMO/designee. The Sponsor will immediately conduct an evaluation to determine if the UADE presents unreasonable risk to subjects. If the Sponsor determines that the UADE presents unreasonable risk, part of the study presenting the risk or all of the study will be terminated within 5 working days of the determination, and no later than 15 working days after the Sponsor received notice of the UADE. For non-significant risk device investigations terminated due to an UADE, a sponsor may not resume a terminated investigation without IRB and FDA approval.

ALL AEs that are collected, as determined by the written protocol, should be tracked in the ORSC RSS's template AE tracker or similar document. All AEs will be sent to the Sponsor quarterly, or at minimum annually.

In addition, the PI will report to the Sponsor, within 5 working days, a withdrawal of approval by the reviewing IRB of the investigator's part of an investigation. The Sponsor will notify the FDA of withdrawal of IRB approval.

The PI will report to the Sponsor, within 5 working days, if the device is used without obtaining informed consent. The Sponsor will notify the FDA of use of the device without informed consent.

8.4.6 Serious Adverse Event Reporting

In consultation with the PI, a trained member of the study team will be responsible for conducting an evaluation of a serious adverse event and shall report the results of such evaluation to the Sponsor and the NIH Institutional Review Board (IRB) as per [Policy 801](#).

Abbreviated Title: Mindfulness and Teen Vaping
Version Date: 07/21/2025
NIH IRB#: IRB001855

8.4.7 Events of Special Interest

N/A

8.4.8 Reporting of Pregnancy

A urine pregnancy test will be included in the screening and before each MRI scan. If a participant is pregnant, we will talk to them about their health and options. If the study team is concerned that the participant may not get health care they need, we will discuss the pregnancy with the consenting parent/guardian even if the participant does not want us to. The participant may not participate in this study if she is pregnant.

8.5 Unanticipated Problems

8.5.1 Definition of Unanticipated Problems (UP)

Any incident, experience, or outcome that meets all of the following criteria:

- Unexpected in terms of nature, severity, or frequency given (a) the research procedures that are described in the protocol-related documents, such as the Institutional Review Board (IRB)-approved research protocol and informed consent document; and (b) the characteristics of the participant population being studied; and
- Related or possibly related to participation in the research (“possibly related” means there is a reasonable possibility that the incident, experience, or outcome may have been caused by the procedures involved in the research); and
- Suggests that the research places participants or others (which many include research staff, family members or other individuals not directly participating in the research) at a greater risk of harm (including physical, psychological, economic, or social harm) than was previously known or expected.

8.5.2 Unanticipated Problem Reporting

The investigator will report unanticipated problems (UPs) to the NIH Institutional Review Board (IRB) as per [Policy 801](#).

9 STATISTICAL CONSIDERATIONS

9.1 Statistical Hypothesis

- Primary Endpoint(s):
 - (1) Our central hypothesis is that frequent nicotine vaping in adolescents will be associated with impaired hippocampal connectivity (measured via s-rsFC) with large-scale brain networks (ECN, DMN, SN) involved in cognitive control and emotion regulation and differences in time in state and state transitions (measured via d-rsFC) between. Alternatively, our null hypothesis is that there will be no difference in the hippocampal connectivity or d-rsFC measures between groups (daily nicotine vaping adolescents and TD age-matched adolescents who do not vape).
 - (2) We hypothesize that the MBSR intervention will increase hippocampal connectivity to the ECN and normalize time in state and state transition measures in vaping adolescents, with

these Δ rsFC predicting Δ vaping behaviors. Alternatively, our null hypothesis is that there will be no change in rsFC or vaping behaviors as a result of the MBSR intervention.

- Secondary Endpoint(s):
 - (1) Descriptive statistics will be calculated to determine the feasibility and acceptability of technology-delivered MBSR, while preliminary efficacy to reduce vaping in adolescents will be assessed with t-tests.

9.2 Sample Size Determination

General fMRI power. Since fMRI is the main outcome measurement utilized in the present protocol, the key power analysis pertains to the fMRI data. However, prospective power analyses for fMRI data are complicated for several reasons. First, fMRI data are analyzed in a hierarchal manner such that both the *intra*-participant variance from the time-course data and the *inter*-participant variance across individuals could affect statistical power. A large number of time points tend to mitigate effects of intra-participant variance, but temporal autocorrelation and scanner limitations limit the number of independent measurements per unit time and thus the number of independent time points that are collected. In addition, effect sizes and both types of variance will vary spatially. Because of this, a given study may have sufficient power to detect differences in some brain regions, but lack sufficient power in other regions where the null hypothesis is false. Finally, fMRI analysis consists of a very large number of non-independent multiple comparisons, greater than 1.5 million at the group level, necessitating correction methods less severe than a Bonferroni correction, as discussed above. Thus, a proper power analysis on fMRI data requires simulating all of these effects. Desmond and Glover⁹⁷ have performed such a simulation. They show for a relatively modest signal change of 0.5% during a cognitive task and with an intra-participant standard deviation of 0.75% and an inter-participant standard deviation of 0.5%, that 11 participants are required for a power of 0.8 using $p < 0.05$. Using a false positive rate of $p < 0.002$, a level more consistent with a cluster size threshold to correct for multiple comparisons⁹⁸, and with the variances kept the same, approximately 21 participants are needed for an expected signal change of 0.5% and 11 participants for a signal change of 0.75%. For more than ~100 independent time points, power (and hence the intra-participant variance) is relatively independent of the number of time points⁹⁷. As signal change is often less than .5% in fMRI studies, we aim to recruit 40 teen vapers and 40 matched control teens for this study.

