9.4.2 Analysis of the Primary Endpoints

Behavioral data analysis: Group differences (Vaping vs. TD) will be evaluated via chi-squares, independent t-tests (Primary Endpoint 1). In addition to EOT nicotine abstinence, Δ scores will be calculated for each behavioral measure (e.g. vaping frequency, emotion regulation) and will be used for within-subject analyses to characterize MBSR-related behavioral change (Primary Endpoint 2).

rsFC fMRI data analysis: Seed-based ROI whole-brain rsFC analyses between *a priori* defined hippocampal seed regions and large-scale brain networks (focusing on DMN, ECN, SN). Whole-brain regression analyses will be conducted for each seed on each individual's preprocessed data resulting in a Fisher-transformed z-value in each brain voxel (**DV**). Seed regions: Right- and left-whole and sub-region hippocampal ROI seeds such as those defined via probabilistic voxel maps created by Chase *et al.*⁹⁹ will be used for rsFC analyses. Target network identification: Hypothesis-driven seed-based analyses will be constrained to voxels within each of three functionally generated masks of large-scale brain networks (DMN, ECN, SN) identified via group independent component analysis⁶ or taken from a published atlas.

s-rsFC Analysis: Independent and Paired t tests will examine group (Vaping vs. TD) (Primary Endpoint 1) and session (Pre/Post-MBSR) (Primary Endpoint 2) effects in s-rsFC strength between each hippocampal seed and voxels within each of the 3 network masks (e.g., seed-ECN voxels).

d-rsFC Analysis: d-rsFC will be estimated using a sliding window method^{21,22} creating windowed correlation matrices, to which a k-means clustering algorithm will be applied to identify states.⁶ Independent and Paired t-tests will examine group (Vaping vs. TD) (Primary Endpoint 1) and session (Pre vs. Post-MBSR) (Primary Endpoint 2) differences in d-rsFC DVs: state occupancy and transitions.

Correlational analyses: To test relationships between MBSR-related Δ rsFC and Δ vaping behaviors and other behavioral outcomes, we will use regression analyses.

Post-hoc analyses: Post-hoc ROI seed-based whole-brain connectivity analyses will test if the regions showing mindfulness-related Δ rsFC are distinct from or overlap with regions modulated by nicotine exposure (from Primary Endpoint 1).

Abbreviated Title: Mindfulness and Teen Vaping

Version Date: 07/21/2025

NIH IRB#: IRB001855

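### The power argument for 40 + 40 describes a one-sample task-activation test, not the study's two-group and paired connectivity tests, and Section 9.4 specifies no multiplicity control for those tests

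*Combined protocol and SAP*

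**What the plan says.** Section 9.2 (Sample Size Determination) holds the only power argument. It draws on a published simulation: "They show for a relatively modest signal change of 0.5% during a cognitive task", with an intra-participant "standard deviation of 0.75% and an inter-participant standard deviation of 0.5" (percent), "11 participants are required for a power of 0.8" at p<0.05. At p<0.002, described as "a level more consistent with a cluster size threshold to correct for multiple comparisons", it gives about 21 participants for a 0.5% change and 11 for a 0.75% change. The step to the study's own size is one sentence: "As signal change is often less than .5% in fMRI studies, we aim to recruit 40 teen vapers and 40 matched control teens". No effect size, SD or power is attached to 40 + 40. On multiplicity, 9.2 describes fMRI comparisons as "necessitating correction methods less severe than a Bonferroni correction, as discussed above".

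Section 9.4.2 (Analysis of the Primary Endpoints) defines the outcome as a Fisher-transformed z in each voxel. Independent t-tests (Endpoint 1, vaping versus non-vaping) and paired t-tests (Endpoint 2, before versus after MBSR) examine "effects in s-rsFC strength between each hippocampal seed and voxels within each of the 3 network masks". The seeds are "Right- and left-whole and sub-region hippocampal ROI seeds", with a published parcellation offered as an example and no count. The same two kinds of t-test are applied to state occupancy and transitions. The scan session in Section 8.2 consists of an anatomical scan, a 10-minute resting-state scan and diffusion imaging.

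**The concern.** A sample-size section should describe the tests that the study will run. This one describes activation in a task that the study does not include, on a percent-signal scale that the primary outcome does not use, and the cited numbers look like single-group requirements. A reader who compares 21 with 40 would think the two-group comparison has nearly twice the participants it needs at the stricter threshold.

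Section 9.2 also relies on a correction for multiple comparisons that it says was discussed earlier. No such discussion appears in the preceding text, and the analysis sections that follow do not supply one. Two primary endpoints, several seeds, three networks and at least two dynamic measures leave many routes to a nominally significant primary result. The seed list, the source of the masks (group ICA or an atlas) and the number of k-means states are open, so the family of tests is undefined as well as unadjusted.

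**Working it through.** **Inputs from Section 9.2.** Signal change 0.5% or 0.75%; inter-participant SD 0.5%; intra-participant SD 0.75%; about 100 independent time points; power 0.8; alpha 0.05 or 0.002. Sidedness is not stated; two-sided is assumed.

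**Step 1: reproduce the plan's figures.** The SD of a participant's mean signal is sqrt(0.5² + 0.75²/100) = sqrt(0.25 + 0.005625) = 0.506%. The standardised effects are 0.5/0.506 = 0.99 and 0.75/0.506 = 1.48. I took the smallest n with exact noncentral-t power of at least 0.8. The one-sample test has n−1 df and noncentrality d·sqrt(n). The two-sample test has 2n−2 df and noncentrality d·sqrt(n/2).

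| Change, alpha | Stated | One-sample n | Two-sample n per group |
|---|---|---|---|
| 0.5%, 0.05 | 11 | 11 | 18 |
| 0.5%, 0.002 | 21 | 21 | 35 |
| 0.75%, 0.002 | 11 | 12 | 17 |

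The one-sample reading matches within one participant; the two-sample reading misses all three. (One-sided one-sample gives 8, 19 and 11, which misses the first.) The document never says one-sample; that is inferred from the match.

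**Step 2: apply this to the primary tests.** Endpoint 1 is a two-sample test, so neither the formula nor the percent-signal inputs apply. Endpoint 2 is paired, which is a one-sample test on differences: the formula carries over, but the signal change and SDs do not describe a change in Fisher-z.

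**Step 3: borrow the inputs anyway.** If 0.506% were the SD of a group comparison, two-group power at 40 per group and p<0.002 would be 0.88 at a 0.5% difference, 0.80 at 0.46%, 0.78 at 0.45%, 0.63 at 0.40% and 0.30 at 0.30%. The 80% point is 0.907 × 0.506 = 0.459%. At alpha 0.05 it is 0.634 × 0.506 = 0.32%. For a paired difference with the same SD at p<0.002 it is 0.662 × 0.506 = 0.33%.

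**Step 4: what n = 40 detects at 80% power, two-sided.**

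| Test | 0.05 | 0.05/3 | 0.002 |
|---|---|---|---|
| Two groups of 40, d | 0.63 | 0.74 | 0.91 |
| Paired, 40 pairs, dz | 0.45 | – | 0.66 |

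**Step 5: multiplicity.** Suppose each seed-by-network search is perfectly corrected within its map and held at 0.05. With independent searches, family-wise error is 1 − 0.95^m. The plan gives no seed count. Assuming 2 seeds × 3 networks, m = 6 and the error is 1 − 0.735 = 26%. Assuming 4 seeds × 3 networks, m = 12 and it is 1 − 0.540 = 46%. These are for one endpoint, before any dynamic measure. With an assumed common correlation of 0.5 between tests, simulation gives about 21% and 32%.

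**The case against.** The study is labelled a pilot and natural-history study, its objectives are to characterise, and it is meant to inform later controlled trials; formal power matters less there. That stands as a reason for restraint. But Section 9.1 states null hypotheses for both primary endpoints and 9.2 presents a key power analysis, so the justification should fit the tests.

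A reader might infer that 40 per group is too few, or that the design lacks 80% power for any signal below 0.5%. The documents do not support either. On the borrowed inputs, two-group power at p<0.002 stays at or above 0.80 down to about 0.46%, and the paired test does better. Since those inputs do not transfer to Fisher-z, neither adequacy nor shortfall can be read from them.

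A reader might also infer that the tests will be run wholly uncorrected and that a false positive is nearly certain. Section 9.2 says correction is necessary and ties p<0.002 to a cluster-size threshold, and 9.4.2 confines the hypothesis-driven tests to three masks. What can be said is that Section 9.4 specifies no correction. The error rates in Step 5 are upper figures: whole-hippocampus and sub-region seeds overlap and all tests share participants, so independence is unlikely.

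**Conclusion.** The point holds in two parts. First, the 9.2 figures belong to a one-sample test of task activation. They do not apply to Endpoint 1 in form or inputs (about 35 per group rather than 21 at p<0.002), nor to Endpoint 2 in inputs. The choice of 40 + 40 follows from no stated calculation. This is a defect of justification, not a demonstrated lack of power. Second, 9.4.1 and 9.4.2 specify no alpha, no within-map threshold and no adjustment across seeds, networks, dynamic measures or the two endpoints. Even with perfect within-map control, the family-wise error for one endpoint could be up to 26% (6 searches) or 46% (12 searches); dynamic measures and the second endpoint would add to it. These sizes rest on two-sided tests, a 0.05 level that the plan does not state for the primary tests, assumed seed counts and independence.

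**What to change.** 1. In 9.2, replace the task-activation figures with what 40/40 detects at 80% power, two-sided: two-group d = 0.63 (alpha 0.05), 0.74 (0.05/3) and 0.91 (0.002); paired dz = 0.45 (0.05) and 0.66 (0.002). Remove the reference to an earlier discussion of correction, or supply that discussion.

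2. In 9.4.2, fix the seed list, the network masks and the number of states before analysis. Specify cluster correction within each map, and Holm or FDR across seeds, networks and dynamic measures within each primary endpoint. Static and dynamic connectivity both stay primary. State whether error is also controlled across the two endpoints. Naming one lead contrast, such as hippocampus–ECN for Endpoint 2 (the network named in the second hypothesis), is optional.

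Cost: a protocol amendment with IRB approval, a less favourable stated sensitivity and stricter thresholds for the primary tests; no extra participants or scans. It should be in place before any analysis, including the abstract analyses that 9.4.6 allows, because prespecification cannot be restored once the maps have been seen.

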9.3 Populations for Analyses

- Modified Intention-to-Treat Analysis Dataset: All frequent nicotine vaping participants approved to participate in the MBSR intervention who complete the first scan day will be included in the comparison of vaping to non-vaping teens. Non-vaping teens who complete the scan will be included in this analysis.
Frequent nicotine vaping participants who completed the study intervention (regardless of number of sessions actually attended) and complete both MRI scans will be included in the pre-post imaging comparison in the vaping group. If they also complete at least one follow-up visit, they will be included in the assessment of effect of MBSR on vaping and related outcome measures.

